3.5.6 Exclusion criteria

The patient will not be enrolled in the study if she/he:

- is unwilling to participate or unable to communicate and give consent (the consent may also be given by her/his legal representative, or by specific consent procedures, acceptable according to the local ethical review process);
- has a contraindication for the COVID-19 (for CVE) or influenza (for IVE) vaccination;
- cannot be swabbed due to severe septum deviation, obstruction or other conditions that contra-indicate swabbing:
- has a history of hospitalisation within the 14 days immediately prior to this admission (including transfers from another hospital);
- had his/her SARI onset ≥ 48 hours after admission to the hospital (for IVE) or ≥ 7 days after admission to the hospital (for CVE);
- was institutionalised at the time of symptom onset (lives at a care-home/residence for people who require
 continual nursing care and have difficulty with the required activities of daily living);
- had a respiratory specimen taken ≥ 8 days after SARI symptom onset (for IVE) or ≥ 10 days after SARI symptom onset (for CVE);
- had a respiratory sample taken ≤ 3 days before SARI symptom onset (for CVE)
- tested positive for any influenza virus in the current season before the onset of symptoms leading to the current hospitalisation (IVE).

Information will be collected on these and other potential exclusion factors and patients will be excluded from primary analyses according to available evidence on these factors (not all available at time of writing).

In sensitivity analyses, the CVE/IVE will be estimated:

- with different cut-offs for numbers of days between onset and swabbing, onset and hospitalisation, and between vaccination and onset of symptoms;
- excluding those positive for seasonal coronaviruses (e.g. HCoV-NL63, HCoV-229E, HCoV-OC43 and HCoV-HKU1):
- excluding those who are current controls (SARS-CoV-2 negative for CVE; influenza negative for IVE) but were
 positive by PCR in the previous year before the current hospitalisation, or reported clinically confirmed COVID19, so as to determine the best cut-off period for having had a previous positive test during the preceding
 year versus 'any previous positive test' irrespective of date;
- using results from rapid antigen tests (RATs) when PCR information unavailable;
- dropping SARS-CoV-2-positive controls from IVE analysis and dropping influenza-positive controls from CVE analysis;
- excluding those who have received antivirals ≤14 days prior to swabbing (to avoid false negatives; the exact cut-off and types of antivirals will be determined as more research becomes available).

Please see Annex 2 for further analysis.

> The study site/country should define how they obtain informed consent from those who are too unwell at time of recruitment (e.g. oral consent with witness for those in isolation, until written consent possible, and/or consent of next of kin by telephone, etc).

[figure not shown]

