3.13.2 Sensitivity analyses

As sensitivity analyses, study sites can measure CVE/IVE:

- with different cut-offs of numbers of days between onset and swab;
- with different cut-offs of numbers of days between vaccination and symptom onset;
- with varying the post-vaccination periods (e.g. 7 days, 14 days, etc.) to be considered 'completely vaccinated' or 'partially vaccinated' (see Section 3.8.1);
- including, excluding, stratifying or adjusting by previous positive test status, and also by different delays between prior test and inclusion in the study:
- excluding patients testing positive prior to hospitalisation but negative in hospital;
- · using only controls positive to other respiratory viruses;
- excluding controls testing SARS-CoV-2 positive (IVE) or influenza positive (CVE), or adjusting by COVID-19 vaccination (see also Section 5.1.7);
- using different reference groups for VE estimation (e.g. for CVE: unvaccinated people, people vaccinated with a smaller number of doses, people vaccinated in the previous season).
- 3.13.3 Pooled analysis.

The higher sample size for the pooled analysis will provide more precision around the VE estimates. Data can be coded as outlined in Annex 1, or a codebook can be provided by the study teams that includes the variable names, descriptions and coding. The central hub will perform data cleaning and document and share any further data cleaning and analysis with all study coordinators to ensure it can be reproduced.

See Annex 2 for details of the pooled analysis plan. For the pooled data, interim analyses will be conducted during different periods, if appropriate, and according to the available sample size.

The timing to conduct each interim analysis will depend on the time needed to achieve the appropriate sample size. This will depend mainly on the incidence of hospitalisation, COVID-19/influenza incidence, vaccination coverage, the recruitment strategy within hospitals and the number of participating hospitals/services per hospital.

The pooled analysis will be carried out in a similar way to the site-specific analysis. Country or study site will potentially be included as a fixed effect, or as a random effect in a multi-level model. Statistical heterogeneity between study sites will be determined in a two-stage analysis using the Q-test and the I² index [30].

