Annex 2. Detailed pooled analysis plan

Pooled analysis outline

A pooled analysis is part of the primary objectives of the ECDC study. Country will be included potentially as a fixed effect or as a random effect in a multi-level model. Statistical heterogeneity between study sites will be determined, using the Q-test and the I^2 index [30].

Cases and controls will be described by baseline characteristics, and uni- and multivariable analyses performed as described in Section 3.13.1 for individual country level analysis.

Pooled analysis plan

Descriptive analysis

The proportion of eligible hospitalised cases and controls who agreed to participate in the study will be calculated. The proportion of patients not consenting will be documented. Patients excluded will be described in a study flowchart.

Patient inclusion depends on the SARI case definition(s) used for CVE and IVE estimates. Sensitivity analyses comparing CVE and IVE estimates based on alternative SARI case definitions are planned. In the primary analysis, CVE is estimated among SARI patients as defined in Section 3.5.2, while IVE is estimated among SARI patient defined as a hospitalised person with:

• at least one systemic symptom or sign: fever or feverishness, malaise, headache or myalgia or deterioration of general condition (asthenia or loss of weight or anorexia or confusion or dizziness);

AND

at least one respiratory symptom or sign (cough, sore throat or shortness of breath)

on admission or within 48 hours after admission. The symptoms should not have started (or clearly worsened, if chronic) more than seven days before swabbing.

Cases and controls will be described by baseline characteristics.

The main characteristics of each study will be summarised individually, and will include:

- Number of hospitals participating and catchment population;
- Beginning of vaccination campaigns for COVID-19 and for influenza vaccines;
 - Beginning of the study:
 - End of the study:
 - Vaccine product(s) used;
 - Estimated vaccine coverage in the country/region by vaccine brand, by target vaccine group;
- Number of patients screened:
- Number of patients excluded per reasons for exclusion.

Measure of effect

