This study is a case—control study (test-negative design). The measure of association is an odds ratio (OR). This can be measured by logistic regression. An OR = 1 indicates no association between an exposure and the outcome. An OR > 1 indicates a potential risk factor, an OR < 1 indicates a potential protective factor, noting that the confidence interval around the OR helps with its interpretation.

For vaccination as preventive factor, the VE can be computed as VE = (1 - OR)*100. A 95% confidence interval is computed around the point estimate.

Pooled univariable analyses (VE estimates from crude OR)

Baseline characteristics of cases and controls will be compared using the chi-square test, Fisher's exact test, t-test or the Mann-Whitney test (depending on the nature of the variable and the sample size). The association (OR) between vaccination status and baseline characteristics will be measured for both case and control groups.

Stratified analysis

Depending on sample size, the analysis by vaccine product will be further stratified according to:

- sex:
- age group, e.g. 0–14 years, 15–49 years, 50–64 years, 65–79 years, 80+ years;
- specific chronic conditions (e.g. respiratory disease, diabetes, immunodeficiency⁹);
- absence, presence of at least one, presence of more than one high-risk condition;
- time: this will depend on timing of the pandemic/influenza season at sites/in countries and may just include one period at the start of the study once vaccines are available, and a specified period later on;
- dose (for CVE): partial vaccination, full vaccination, full vaccination plus booster;
- swab delay (0–3 days, 4–7 days; 8+ days);
- vaccination delay (<8 days, 8–14 days, >14 days, etc.);
- hospital admission delay (0-4 days, 5-9 days, 10 days +, onset after hospitalisation);
- previous vaccination against influenza and pneumococcal disease;
- prior infection with influenza or SARS-CoV-2 (prior to hospital admission for SARI);
- current co-infection with influenza (for CVE) or SARS-CoV-2 (for IVE) or other respiratory viruses (for both CVE and IVE);
- severity (ICU admission, ventilation/oxygen, death; for CVE);
- CVE/IVE at different time points in calendar time, e.g. by week or group of weeks (e.g. CVE for weeks 2–20, 21–42, etc.; IVE for interim season (to end January), and for the whole season);
- for the various groups of vaccines (if available/applicable), mode of injection (intradermal vs intramuscular);

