 - considering those vaccinated <X days before onset of symptoms as unvaccinated (in the main analysis these records will be excluded);
 - including SARI patients testing positive for influenza/SARS-CoV-2 in the control group;
 - including SARI patients testing positive for influenza/SARS-CoV-2 in the case group;
 - including SARI patients whose influenza/COVID-19 vaccine status is unknown in the control group;
 - using, as a control group, only SARI patients testing positive for at least one non-influenza respiratory virus/non-coronavirus;
 - considering different restrictions according to swabbing delay (e.g. <14 days, <10 days, etc.);
 - considering the sensitivity and specificity of PCR;
 - based on assumptions of previous infections;
 - excluding participants who received antivirals ≤14 days prior to swabbing;
 - excluding all participants with lab-confirmed influenza/SARS-CoV-2 at any time after symptom onset, to reduce bias.
- This can then be repeated using RSV as a sham outcome (if multiplex results are available for any sites).
 There should be no association between COVID-19/influenza vaccination and RSV-positivity in the absence of confounding.

Time can be input as a variable in the model to assess whether it can be an effect modifier.

Minimum sample size

Sample sizes may be very small for some sub-analyses. Different criteria can be used to determine whether the sample size is large enough to obtain a valid measure of VE;

- there are at least 10–15 cases (or controls, whichever is smaller) in the sub-analysis for crude analyses and more for adjusted analyses (e.g. at least 10 for each parameter in the model);
- there are ≥5 records in each cell of the two-by-two table of case and vaccination status;
- the precision of the estimate does not span both -200% and 90% (uninformative).

With low sample size, approaches include collapsing categories, or modelling continuous variables in a different way (if applicable). Sensitivity analyses can be carried out using penalised logistic regression.

Use of propensity scores

To limit the number of co-variables to include in the multivariable model, **if sample size allows**, estimates will be built and adjusted based on propensity scores. Propensity scores can be defined as the conditional probability of receiving the vaccine given a number of observed co-variables.

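### Section 3.5.6 gives two incompatible rules for late-swabbed patients, and the Annex 2 swab-delay analyses beyond the primary limit work as planned under only one of them

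*Protocol*

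**What the plan says.** Section 3.5.6 introduces its list with "The patient will not be enrolled in the study if she/he". One listed item is that the patient "had a respiratory specimen taken ≥ 8 days after SARI symptom onset (for IVE) or ≥ 10 days after SARI symptom onset (for CVE"). Directly after the list, the same section says: "Information will be collected on these and other potential exclusion factors and patients will be excluded from primary analyses according to available evidence". It then asks for sensitivity analyses "with different cut-offs for numbers of days between onset and swabbing, onset and hospitalisation, and between vaccination and onset of symptoms", and section 3.13.2 repeats this for sites: "with different cut-offs of numbers of days between onset and swab". Neither place says whether the cut-offs are to be wider or narrower.

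Annex 2 is more specific. Its sensitivity list includes "considering different restrictions according to swabbing delay (e.g. <14 days, <10 days, etc".), and its stratified analysis includes "swab delay (0–3 days, 4–7 days; 8+ days"). For IVE it also puts a swab limit inside the SARI definition used for the primary analysis: "The symptoms should not have started (or clearly worsened, if chronic) more than seven days before swabbing".

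Three other places bear on the point:
- Section 3.5.2 includes patients with onset in the 14 days before admission, and says that a swab-delay cut-off might be set in a later protocol version.
- Section 3.6 asks for swabbing within 48 hours of admission.
- Annex 3 names an onset-to-swab delay of at most 10 days among the criteria for inclusion in the pooled analysis.

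**The concern.** A patient cannot be both kept out of the study and held in the dataset but dropped from one analysis. The choice matters because Annex 2 names analyses that reach past the primary limits. Those analyses need the patients whom the lead-in turns away.

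Section 5.2 says that the lag between onset and specimen collection may affect positivity rates between sites. The wider cut-offs and the 8+ day stratum are where the plan would examine late swabs. If some sites follow the lead-in and others the paragraph after the list, the extra patients in those analyses come only from the second group of sites. Countries write their own protocols from this core text (section 1.5), so both interpretations could be adopted in good faith. A patient who was never enrolled cannot be recovered at the analysis stage.

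**Working it through.** The plan states no figure on this point, so there is none to reproduce. The check compares sets of whole-day delays.

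**Inputs**
- Delay d = swab date minus onset date, in days.
- Primary limits (3.5.6): IVE keeps d < 8, that is days 0–7. CVE keeps d < 10, that is days 0–9. The Annex 2 IVE definition (onset not more than seven days before the swab) also gives days 0–7.
- Largest delay expected: 14 days from onset to admission (3.5.2) plus 2 days to swab (3.6) = 16 days. The conclusion does not depend on this maximum.
- Planned cut-offs: <10 and <14 days. Planned strata: 0–3, 4–7 and 8+ days (Annex 2).

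**Two rules**
- Rule A (lead-in): late-swabbed patients are not enrolled, so the dataset is the primary set.
- Rule B (paragraph after the list): they are recorded and left out of the primary analyses only, so the dataset covers days 0–16.

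Each analysis uses the overlap of its own day range with the dataset.

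| Analysis | Rule A | Rule B |
|---|---|---|
| IVE <10 | 0–7, same as primary | 0–9, adds 8–9 |
| IVE <14 | 0–7, same as primary | 0–13, adds 8–13 |
| IVE 8+ | empty | 8–16 |
| CVE <10 | 0–9, same as primary | 0–9, same as primary |
| CVE <14 | 0–9, same as primary | 0–13, adds 10–13 |
| CVE 8+ | 8–9 only | 8–16 |
| 0–3 and 4–7, both vaccines | complete | complete |

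**Narrower cut-offs** differ from the primary set under both rules. For example, IVE <7 drops day 7, and CVE <8 drops days 8–9.

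**Qualification for IVE under rule A.** The limits are vaccine-specific, so a patient swabbed on day 8 or 9 can be enrolled for CVE. Section 3.5.5 advises all sites to test for both viruses in the influenza season. Such a patient may therefore carry an influenza result in a shared dataset. At a site running both studies, IVE <10, IVE <14 and IVE 8+ could then hold days 8–9, but nothing later.

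**Boundary check.** Section 3.5.6 excludes CVE patients at d ≥ 10, so day 9 is the last day kept. The Annex 3 criterion (at most 10 days) keeps day 10. The two differ by one day.

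**The case against.** The strongest reply is that most of the protocol treats swab delay as an analysis-stage criterion, so rule B is probably what is meant. Annex 3 starts from all recruited positive cases and then, where possible, removes those who could later be left out of a pooled analysis, with swab delay as an example. That presupposes that late-swabbed cases are recruited. Annex 2 places the seven-day IVE limit in the primary-analysis definition. Section 3.5.2 sets no swab limit and treats one as still open. This reply stands as evidence of intent. It does not remove the lead-in, which is worded as an instruction about enrolment.

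A reader might infer three stronger things, and the documents support none of them.
- *That the wider cut-offs must return the primary estimate.* This follows only where a site obeys the lead-in. Under the paragraph after the list, IVE <10, IVE <14 and CVE <14 all add patients. CVE <10 coincides with the primary rule in any case, so its redundancy is not caused by non-enrolment.
- *That the primary pooled estimate is compromised.* Applying the stated limits at analysis gives the same primary set whichever sentence a site followed.
- *That the plan hides a large bias from false-negative controls.* The protocol does not name late swabs as a main source of these. Section 5.1.8 names antivirals and test performance. Section 5.2 says only that the lag may affect positivity.

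The suggested results layout (Table 7) shows case and control numbers, so two identical sets would be visible to a careful reader. The inclusion-algorithm figures are not shown in the text available, so it could not be checked whether they screen on swab delay.

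**Conclusion.** The inconsistency is real and limited in reach. For sites that follow the lead-in, CVE <14 adds no one, CVE 8+ is cut to days 8–9, and the IVE <10, <14 and 8+ analyses gain at most days 8–9 through patients also enrolled for CVE. For sites that follow the paragraph after the list, all of these work except CVE <10, which is merely redundant. The effect on the pooled secondary analyses depends on how many sites follow each sentence and how many patients are swabbed late. The protocol gives neither number, so no patient count or shift in vaccine effectiveness can be stated. The conclusion assumes that each site applies one of the two sentences as written. It is worth correcting before recruitment, because the loss cannot be repaired afterwards.

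**What to change.** 1. In section 3.5.6, list specimen delay under a separate category: enrolled and recorded, but left out of the primary analysis. For every other listed criterion, state whether it bars enrolment or only primary analysis. This covers consent, contraindication, inability to be swabbed, recent hospitalisation, in-hospital onset, institutional residence, a sample taken before onset, and prior influenza positivity in the season.
2. In Annex 2, state that cut-offs beyond the primary limit and the 8+ day stratum use these retained patients. Drop <10 days as a sensitivity cut-off for CVE.
3. Reconcile section 3.5.2 (cut-off still to be set) and Annex 3 (at most 10 days) with the limit of 10 or more days in section 3.5.6.

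The cost is protocol wording, plus records on some additional late-swabbed patients whose number the protocol does not allow one to estimate. Onset and swab dates are already Annex 1 variables, so no new data items are needed.

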3.5.2 SARI patient

A SARI patient is defined as a hospitalised person with at least one of the following symptoms:

- cough;
- fever;
- shortness of breath;
- sudden onset of anosmia, ageusia or dysgeusia.

SARI patients with onset of symptoms in the 14 days prior to hospital admission will be included in the study. Note that hospitals already participating in SARI surveillance systems should not modify the SARI inclusion criteria for surveillance. However, for the CVE analysis, only those patients with onset of symptoms in the 14 days prior to hospital admission will be included.

In a later protocol version, a cut-off for days between onset of symptoms and swabbing may be decided (if appropriate).

A SARI patient is defined using ECDC's clinical case definition for a hospitalised possible COVID-19 case³. Compared with the World Health Organization (WHO) SARI case definition⁴ (an acute respiratory infection with a history of fever or measured fever of ≥38 C° and cough, onset within the last 10 days and requiring hospitalisation), ECDC's possible COVID-19 case definition is more sensitive. Each study site/country will report individual SARI symptoms separately to allow sensitivity analyses comparing CVE and IVE estimates, based on alternative SARI case definitions and depending on the pathogen.

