3.5.3 SARI patients confirmed as COVID-19

A confirmed COVID-19 case will be defined as a hospitalised patient fulfilling the SARI case definition, with a respiratory sample positive for SARS-CoV-2 by PCR, [29] either on admission to hospital or documented in the 14 days prior to hospital admission.

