3.6 SARI patient identification – algorithm for patient inclusion

SARI patients are identified from among patients hospitalised for at least 24 hours in one of the participating hospitals. SARI patients should be enrolled and swabbed within 48 hours of hospital admission.

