3.12.2 Data checking and cleaning

Data checking will be carried out at the study site level. Summary and frequency tables as well as visual representations of appropriate variables are used to find illegal, implausible or missing values within the dataset. Checks for inconsistencies are carried out (e.g. date of swab before date of symptom onset). These values should be checked against the questionnaires or queried against the hospital record. Any missing data will be described.

Any changes or recoding to the data during the cleaning process (e.g. age to age groups) are documented and stored separately from the crude database. Guidance and/or example scripts for data cleaning can be provided if so desired.

Data checking is an iterative process (see Annex 3). After checking, data will be cleaned and stored separately from the source data. All changes to the data will be documented in scripts.

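### The pre-onset swab exclusion for CVE (Section 3.5.6) runs the wrong way: it drops samples taken 1–3 days before onset and sets no limit on earlier ones

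*Protocol*

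**What the plan says.** All references are to the Protocol.

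- **Pre-onset limit, Section 3.5.6.** A patient is not enrolled if she or he "had a respiratory sample taken ≤ 3 days before SARI symptom onset (for CVE". No other item in the list limits how long before onset a CVE sample may be taken.
- **Post-onset limit, same list.** A specimen is ruled out if taken "≥ 10 days after SARI symptom onset (for CVE".
- **Case definition, Section 3.5.3.** The qualifying PCR positive may be obtained "either on admission to hospital or documented in the 14 days prior to hospital admission".
- **Onset window, Section 3.5.2.** For the CVE analysis, "only those patients with onset of symptoms in the 14 days prior to hospital admission will be included".
- **Onset after admission, Section 3.5.6.** The list rules out onset only from "≥ 7 days after admission to the hospital (for CVE", which is wider than Section 3.5.2.
- **Study swab, Section 3.6.** "SARI patients should be enrolled and swabbed within 48 hours of hospital admission". Section 3.5.5 requires a control's negative sample to be the one taken on admission.
- **Data check, Section 3.12.2.** "Checks for inconsistencies are carried out (e.g. date of swab before date of symptom onset"; such values are then checked or queried at source.

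**The concern.** A limit on the gap between swab and onset is there to keep samples that plausibly belong to the SARI episode. The post-onset limit does this. The pre-onset limit does the reverse: it removes the samples closest to onset and lets through those whose link to the illness is weakest. The retained range of delays has a hole just before day 0 and runs on below it, and the protocol gives no reason for that shape.

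Two things are at stake. A SARS-CoV-2 infection unrelated to the SARI episode can enter the primary CVE analysis as a case, which dilutes the estimate. And because this is a core protocol that each country implements before pooling, some sites may code the rule literally while others code what they think was meant, so eligibility would no longer be common across sites.

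**Working it through.** The point turns on the direction of an inequality, and the plan gives no figure to reproduce. I listed the delays that the protocol's own windows allow and applied the rule to them.

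**Inputs.** Day 0 is admission and d = swab day − onset day, so negative d means the swab came before onset.

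- Case swab: day −14 to +2 (14 days before admission, Section 3.5.3; within 48 hours after, Section 3.6).
- Control swab: day 0 to +2 (Sections 3.5.5 and 3.6).
- Onset: day −14 to 0 (Section 3.5.2), or −14 to +6 if the wider allowance in Section 3.5.6 applies.
- Post-onset rule: d ≥ 10 excluded (Section 3.5.6).
- Pre-onset rule as written: d = −1, −2, −3 excluded.

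**Result as written.**

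| Onset window | Group | Kept d | Excluded as pre-onset |
|---|---|---|---|
| −14 to 0 | Cases | −14 to −4, and 0 to 9 | −3 to −1 |
| −14 to 0 | Controls | 0 to 9 | none arise |
| −14 to +6 | Cases | −20 to −4, and 0 to 9 | −3 to −1 |
| −14 to +6 | Controls | −6 to −4, and 0 to 9 | −3 to −1 |

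If the day of onset also counts as caught, d = 0 moves to the excluded column in every row.

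**Example.** Take two patients with onset on day −1. A PCR positive on day −12 gives d = −12 − (−1) = −11, which this rule keeps. A positive on day −2 gives d = −2 − (−1) = −1, which it excludes.

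**Result with the direction reversed.** Excluding samples more than 3 days before onset leaves one continuous range, d = −3 to 9, for cases under either onset window. Excluding 3 or more days before onset leaves d = −2 to 9.

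**Illustration of the bias.** Assumptions: coverage in controls 50% (odds 1), true OR 0.5 (VE 50%), and unrelated cases vaccinated at the control rate. True cases then have vaccination odds of 0.5 × 1 = 0.5, a coverage of 0.5/1.5 = 1/3. With a share p of unrelated cases, case coverage is (1 − p)/3 + 0.5p.

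- p = 5%: 0.3167 + 0.0250 = 0.3417; OR = 0.3417/0.6583 = 0.519; VE = 48.1%.
- p = 10%: 0.3000 + 0.0500 = 0.3500; OR = 0.3500/0.6500 = 0.538; VE = 46.2%.

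**The case against.** The best case for leaving the rule alone is that little passes through the gap, and parts of this stand.

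- **The admission swab.** Every SARI patient should be swabbed within 48 hours of admission. If that swab is also positive, case status does not depend on the early sample. This narrows the problem to cases resting on the pre-admission positive alone.
- **The sensitivity analysis in Section 3.13.2.** It lists dropping patients who were positive before hospitalisation but negative in hospital, which is exactly that group. It is something sites can do, however, and it leaves the primary analysis unchanged.
- **The 60-day rule in Section 3.9.9.** It removes recent positives from the primary analysis but gives no reference date. It may or may not remove the day −12 patient, so one cannot say flatly that this patient ends up as a case. If the rule covers the 14 days before admission, it collides with the case definition in Section 3.5.3. It does not reach early negatives.
- **Expected numbers.** The swab-delay categories in Table 6 and Annex 2 start at day 0, which suggests that few pre-onset swabs are expected. It also means that any retained have no category.

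A reader might infer more than the documents support:

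- *That negatives from 4–14 days before onset become controls.* Sections 3.5.5 and 3.5.2 together put a control's swab on or after onset. Early negatives arise only under the conflicting post-admission allowance in Section 3.5.6, and then only at 4–6 days.
- *That Section 3.12.2 rejects swabs taken before onset.* It only queries such dates, which is compatible with any eligibility limit.
- *That same-day samples are certainly excluded.* The wording leaves this open.

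None of this changes the direction of the criterion, and no other section sets the missing outer limit.

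**Conclusion.** The criterion is wrong as written. It excludes CVE samples taken 1–3 days before onset and puts no limit on earlier ones. A likely origin is a signed delay of −3 days or less put into words, but that is inference.

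The effect falls mainly on cases resting on a pre-admission positive. The protocol does not say how many there will be. The shift from 50% to about 48% or 46% rests on an assumed 5–10% share of unrelated cases and on the coverage and VE chosen for illustration, so it is modest and indicative only. Losing samples taken 1–3 days before onset costs precision; no bias from that loss has been shown. The reason to correct it is that the rule decides who enters the primary CVE analysis and is to be applied identically across countries.

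It would go too far to say that the intended boundary is known. The documents do not settle whether the cut belongs at more than 3 days or at 3 or more days before onset.

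**What to change.** 1. In Section 3.5.6, reverse the criterion so that CVE samples taken too long before onset are excluded, for example more than 3 days before.
2. Write it as a signed delay, swab date minus onset date, with both ends stated (for example, kept if the delay is −3 to +9 days), so that day 0 is explicit. The sponsor should confirm whether the lower end is −3 or −2.
3. Reconcile it with the onset window in Section 3.5.2 (including the onset-after-admission item in Section 3.5.6) and the 14-day case window in Section 3.5.3, and give the 60-day rule in Section 3.9.9 a reference date.

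Section 3.12.2 needs no change. The cost is one reworded criterion, a few clarifying words in the linked sections and the matching line in the sites' eligibility code. No new data are needed, because onset and swab dates are already collected.
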